### 13.2 Drug and Virus Screening

At the Screening Visit, the urine and blood samples will be taken for:

**Standard Drug Panel:** Urine drug screen for barbiturates, benzodiazepines, opioids, cocaine, cannabinoids, and amphetamines. Result must be negative at Screening.

**Virus Screen:** Serology screen in blood for the detection of antiviral antibodies for human immunodeficiency virus (HIV), hepatitis C virus (HCV) and hepatitis B virus (HBV) surface antigen. Result must be negative at Screening for inclusion into the study.

Sample collection, handling, labeling and shipping should be done following the instructions provided by the relevant certified laboratory and the applicable local regulations.

### 13.3 Urine Pregnancy Tests

The UPTs will be performed at the study site, if the site is registered and conforms to CLIA regulations for such testing (possesses a current valid CLIA Certificate of Waiver), or at an appropriately registered reference laboratory. A UPT will be performed on all females of childbearing potential at Screening, Baseline, and Day 14 (or EOS). The investigator will report the UPT results on the CRFs, in the subject's medical records, and in independent records maintained at the study site. The UPT used must have a minimum sensitivity of 25 mIU of  $\beta$ -HCG/mL.

### 13.4 Plasma Sample Collection

One of the objectives of the study is to determine the trough plasma concentrations of cortisone 17 $\alpha$ -propionate and cortisone associated with the topical application of CB-03-01 cream, 1% in subjects with acne vulgaris.

#### *13.4.1 Plasma Sample Collection*

Blood will be collected at each visit (Screening, Baseline, Day 7, and Day 14) immediately prior to the application of the test article (if applicable). Concentrations of cortisone 17 $\alpha$ -propionate and cortisone will be determined. The method of blood sample collection for

---

 Females of childbearing potential are defined as subjects who have experienced menarche or are 10 years of age or older.

through PK analysis is detailed in the laboratory manual to be provided by the bioanalytical laboratory.

#### ***13.4.2 Plasma Storage***

[figure not shown]
Each plasma sample will be divided into two pre-labeled and pre-cooled polypropylene tubes and placed on dry ice and acetone until final storage in an ultra-low freezer as specified in the laboratory manual.

Each sample tube will be identified with a label resistant to storage temperature. Please refer to the laboratory manual for specific instructions related to the labeling and management of these specimens.

#### ***13.4.3 Specimen Shipment***

On request, site staff personnel shall ship one of the duplicate samples of plasma frozen under dry ice. The secondary plasma sample will be retained in an ultra-low freezer as specified in the laboratory manual as back-up samples until confirmation that the initial shipment has been received safely by the analytical laboratory.

Samples will be shipped by an authorized courier to:

The study site shall retain copies of the shipping documents generated at the time of shipment. Refer to the laboratory manual for additional detailed instructions related to the labeling and management of these specimens.

#### ***13.4.4 Analytical Methodology***

The concentrations of cortexolone 17 $\alpha$ -propionate (CB-03-01) and cortexolone will be determined in the plasma samples using validated analytical methods for each analyte [4, 5].

### **13.5 Cosyntropin Stimulation Test**

At Visit 1 (Screening), a CST will be performed for each subject between 7 AM and 9 AM.

At Visit 4 (or EOS), a CST (and any follow-up CSTs) will be performed within  $\pm$  one hour of the screening CST and ideally between 7 AM and 9 AM.

Perform the CST as follows (see [Appendix 4](#)):

- Collect a pre-stimulation blood sample as specified in the Laboratory Manual.

- Reconstitute one vial of cosyntropin (0.25mg) in sodium chloride for injection USP (the volume of sodium chloride in the package insert for Cortrosyn® is 2 to 5mL).
- Inject the cosyntropin intravenously (the length of time during which the cosyntropin should be injected is 2 minutes).
- Thirty (30) minutes after completing the cosyntropin injection, collect a post-stimulation blood sample as specified in the Laboratory Manual.

If the results of the Visit 1 (Screening) CST indicate the subject has an abnormal HPA axis response (defined as a post-stimulation serum cortisol level of  $\leq 18 \mu\text{g/dL}$ ), the subject will be classified as a screen failure and withdrawn from the study following the procedures in Section 14.4. In addition, direct the subject to consult with their physician concerning the abnormality unless the investigator believes it is not medically indicated. The conversation with the subject must be documented in the source documents.

If a subject's EOS laboratory results show an abnormal HPA axis response (defined as a post-stimulation serum cortisol level of  $\leq 18 \mu\text{g/dL}$ ), the test article will be considered to have caused the abnormal CST result in the subject. Report this abnormality as an AE. Instruct the subject not to use ANY topical or systemic steroids; however, other therapies that will not affect their adrenal function may be used to treat their acne. The subject should be scheduled to return for a follow-up visit no less than four (4) weeks after the EOS laboratory samples are collected. In the event the subject is still found to have laboratory evidence of adrenal suppression, the subject will be required to return for additional follow-up visits, no less than every four (4) weeks, until the HPA axis response has been documented to return to normal.

AEs that may be associated with the CST and that must be included in the informed consent/assent include:

- Rare hypersensitivity reactions
- Bradycardia
- Tachycardia
- Hypertension
- Peripheral edema
- Rash

AEs associated with venipuncture and that must also be included in the informed consent/assent include those listed in [Section 13.1](#).

#### **14. END OF STUDY CRITERIA**

At the end of each subject's participation in the study, the investigator will complete an End of Study form for all completed and discontinued subjects.

### 14.1 Completion of the Study

Each subject who completes the course of treatment as specified in this protocol will have completed the study.

### 14.2 Subject Discontinuation

A subject may be withdrawn from the study prior to completion for any of the following reasons:

- Whenever the subject or the subject's parent/guardian decides it is in the subject's best interest to withdraw. NOTE: if the subject decides to withdraw from the study due to an AE then it should be classified as withdrawal due to an AE.
- Whenever the investigator decides it is in the subject's best interest to be withdrawn
- AEs
- Progressive disease
- Noncompliance with study drug
- Protocol deviation
- Pregnancy (if applicable)
- Lost to follow-up
- Study terminated by Sponsor
- Death

If a subject withdraws from the study prematurely for any reason, every attempt should be made to complete the EOS procedures prior to discharging the subject from the study. If a subject withdraws prematurely during the treatment period for any reason, the Visit 4 procedures (minus the PK blood draw) will be completed. Subjects who withdraw prematurely will be replaced until at least 20 subjects with both Screening and Day 14 serum cortisol data (pre- and post-cosyntropin stimulation) have completed the study without any significant protocol violations (i.e., evaluable subjects). When a subject is withdrawn from the study for a treatment-related AE (i.e., possibly, probably or definitely related as defined in [Section 15.1](#)), when possible, the subject should be followed until resolution of the AE.

### 14.3 Study Termination

The study may be terminated by the investigator or the Sponsor. If, in the opinion of the investigator, clinical observations made during the study suggest that it may be unwise to continue, he or she may stop the study. A study termination by the investigator will be reported to the Sponsor.

In addition, a written statement fully documenting the reasons for this action will be submitted to the Sponsor by the investigator within five (5) working days.

In the event that the Sponsor chooses to discontinue or terminate the study, appropriate notification will be given to the investigator.

#### 14.4 Screen Failures

A subject will be considered a screen failure if Visit 1/Screening laboratory results indicate (1) an abnormal pre-CST serum cortisol level, (2) abnormal HPA axis function (a low post-CST serum cortisol level), or (3) other clinically significant out-of-range laboratory test results, in the opinion of the investigator. If these conditions apply, the subject should be excluded from study participation, and the Screen Failure CRF should be completed. No clinical evaluation or follow-up CST will be performed in these subjects.

If a subject withdraws prematurely during the treatment period for another reason, complete the CRF for the appropriate visit, then complete the End of Study CRFs including scheduling appropriately to obtain the End of Study CST.

Subject enrollment will continue until at least 20 evaluable subjects with both Screening and Day 14 serum cortisol data (pre- and post-cosyntropin stimulation) have completed the study without any significant protocol violations (evaluable subjects). This may require the enrollment of approximately 24 subjects.

### 15. ADVERSE EVENT REPORTING

An **adverse event** (AE) is any untoward medical occurrence associated with the use of a drug in humans, whether or not considered drug related.

An AE (also referred to as an adverse experience) can be any unfavorable and unintended sign (e.g., an abnormal laboratory finding), symptom, or disease temporally associated with the use of a drug, without any judgment about causality. An AE can arise from any use of the drug (e.g., off-label use, use in combination with any drug) and from any route of administration, formulation or dose, including an overdose.

Information on the medical condition of subjects should begin following the subject's written consent/assent to participate in the study and a medical history should be taken at screening. During any wash out and baseline periods, any changes in the health of subjects should be recorded as changes in medical history unless an event occurred as a result of a study-related procedure and is unanticipated; in such cases, the event should be recorded as an AE and reported to the Institutional Review Board (IRB) or Institutional Ethics Committee (IEC) as an "unanticipated problem" in accordance with local procedures. Other changes in subject health information becomes AE data when the subject begins dosing with the test article and therefore AE data should be collected from the date of the first dose of test article. These data are considered treatment-emergent AEs.

Timely and complete reporting of all AEs assists the contract research organization (CRO) in identifying any untoward medical occurrence, thereby allowing:

- 1) protection of the safety of study subjects;
- 2) a greater understanding of the overall safety profile of the test article;
- 3) recognition of dose-related test article toxicity;
- 4) appropriate modification of study protocols;
- 5) improvements in study design or procedures; and
- 6) adherence to worldwide regulatory requirements.

Test article is defined as a pharmaceutical form of an active ingredient (or “primary operational component” for devices) or vehicle/placebo being tested or used as a reference in the study, whether blinded or unblinded. AEs may be either spontaneously reported or elicited during questioning and examination of a subject. All AEs must be completely recorded on the AE CRF. If known, the investigator should report the diagnosis of the underlying illness or disorder, rather than its individual symptoms. Subjects experiencing AEs that cause interruption or discontinuation of test article, or those experiencing AEs that are present at the end of their participation in the study should receive follow-up as appropriate. If possible, report the outcome of any AE that caused permanent discontinuation or that was present at the end of the study particularly if the AE is considered by the investigator to be treatment-related (i.e., definitely, probably, or possibly related to test article).

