13. Subject has any clinically significant medical abnormality or chronic disease of the cardiovascular, gastrointestinal, respiratory, hepatic, or renal systems. This includes conditions (e.g., gastrointestinal surgery) that may interfere with metabolism or excretion.
14. Subject has a history of alcohol and/or drug abuse in the investigator's judgment or has a positive urine drug screen result at Visit 1 (Screening).
15. Subject is unable to communicate or cooperate with the investigator due to language problems, poor mental development, or impaired cerebral function.
16. Subject is known to be hypersensitive to the test article or any components in the test article (see [Section 6.1](#)).
17. Subject has received an investigational drug or been treated with an investigational device within 30 days prior to Visit 2 (Baseline).

18. Subject is currently enrolled in an investigational drug or device study.
19. Subject has an irregular sleep schedule (cortisol levels exhibit physiological diurnal variation) as judged by the investigator.
20. Subject has experienced significant blood loss, as judged by the investigator, within 60 days or has donated plasma within 72 hours prior to Visit 2 (Baseline).
21. Subject tests positive at screening for human immunodeficiency virus (HIV) or is known to be seropositive for HIV.
22. Subject tests positive at Visit 1 (Screening) for hepatitis B surface antigen, hepatitis C antibody, or has a history of a positive result.
23. Subject had major surgery within 30 days prior to Visit 2 (Baseline) or plans to have surgery during the study.
24. Subject has participated in a prior CB-03-01 clinical trial

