## 18. STATISTICAL CONSIDERATIONS

### 18.1 Sample Size

No formal power calculations were performed to establish the sample size. The number of evaluable subjects is historically consistent with other HPA/PK studies in this age range.

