### **18.3 Statistical Methods**

All statistical processing will be performed using SAS® unless otherwise stated. Excel or SAS® will be used for the analysis of trough plasma concentrations data.

All subjects enrolled in the study who were dispensed and applied test article at least once will be included in the analysis of safety and will be considered the Safety population. Subjects who were discontinued from the study at Visit 2 (Baseline) due to abnormal screening laboratory test results or failure to meet any other eligibility criteria will be classified as screen failures and excluded from the HPA axis suppression summaries. Subjects with both Screening and Day 14 (or EOS) serum cortisol data (pre- and post-cosyntropin stimulation) who completed the study without significant protocol violations will be considered evaluable (Evaluable population). Subjects included in the PK analysis (PK population) must not have any significant protocol deviations, must have at least an 80% dose compliance based on number of applications, and must apply the final three doses as prescribed prior to the EOS PK assessment.

Demographic and baseline characteristics will be summarized for the Safety, Evaluable, and PK populations. In addition, demographic variables, AEs, and primary reason for screen failure will be summarized separately for screen fail subjects. Frequency counts and

percentages will be reported for categorical data and sample size, mean, standard deviation, median, minimum, and maximum will be reported for the continuous variables.

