#### CONTRAINDICATION

The only contraindication to CORTROSYN™ (cosyntropin) for Injection is a history of a previous adverse reaction to it.

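### Section 15 files the listed reactions to the Screening cosyntropin injection as medical history, in conflict with other sections, and no specific criterion or check reflects the contraindication in Appendix 4

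*Protocol*

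**What the plan says.** **Recording.** For the wash-out and baseline periods, Protocol Section 15 states that "any changes in the health of subjects should be recorded as changes in medical history". It allows a single exception, with two conditions that must both be met, and words it as follows: "unless an event occurred as a result of a study-related procedure and is unanticipated". Events that meet the exception are recorded as AEs and also reported to the IRB/IEC as unanticipated problems. For everything else, "AE data should be collected from the date of the first dose of test article".

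Section 13.5 introduces its list of test reactions with the words "AEs that may be associated with the CST and that must be included in the informed consent/assent include". The list covers hypersensitivity, slow or fast heart rate, raised blood pressure, peripheral edema and rash. Section 18.3 promises that "demographic variables, AEs, and primary reason for screen failure will be summarized separately for screen fail subjects".

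**Contraindication.** The cosyntropin label in Appendix 4 states: "The only contraindication to CORTROSYN™ (cosyntropin) for Injection is a history of a previous adverse reaction to it". The only hypersensitivity criterion in Section 5.1.2, number 16, reads: "Subject is known to be hypersensitive to the test article or any components in the test article".

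**The concern.** Cosyntropin is the one drug injected in this trial, and it is given to every child whose screening reaches the CST. The exception in Section 15 joins two conditions. A reaction to the Screening injection meets the first, because a study procedure caused it. If it is one the protocol names in advance, it fails the second. The reactions most clearly attributable to the injection are therefore the ones kept off the AE form.

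Two things are at stake. Sites following different sections would record the same reaction in different places, so the pre-treatment safety record would be incomplete and not comparable across sites. In addition, a reaction at Screening is the kind of history that the appended label treats as a contraindication, and the same injection is scheduled again at Visit 4. No section specifically asks about an earlier reaction before either injection.

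**Working it through.** The plan gives no figure to reproduce: "No formal power calculations were performed to establish the sample size", and no reaction rate is stated. The check is therefore mainly textual, with a simple count for scale.

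**Step 1: timing.** Section 10.2 puts Baseline (Day 1, first dose) 14 to 45 days after the Screening CST. Every Screening reaction arising in that interval thus falls after consent and before AE collection starts. Visit 4 is Day 14 ± 2, that is Day 12 to Day 16, or 11 to 15 days after Day 1. The interval between the two scheduled injections is:
- shortest: 14 + 11 = 25 days
- longest: 45 + 15 = 60 days

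**Step 2: the recording rule applied to a listed reaction.** Take a rash after the Screening CST. Caused by a study procedure: yes. Unanticipated: no, because Section 13.5 requires it to be named in the consent/assent form. The exception fails, so it is recorded as medical history. The same holds for each reaction on the Section 13.5 list. Reactions to the Visit 4 CST come after the first dose and are AEs, so the problem is confined to Screening.

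**Step 3: the passages side by side.**

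| Place | Status of a listed Screening reaction |
|---|---|
| Section 15, pre-dose rule | Medical history |
| Section 15, opening definition (untoward occurrence associated with use of a drug) | AE |
| Section 13.5 | Called an AE |
| Schedule of Events | AE evaluation marked at Screening |
| Section 18.3 | AEs to be summarized for screen failures |
| SAP 6.3 and 7.8.1 | Outside the AE tables, which count only events starting on or after the first dose date |
| SAP 7.7.1 | For screen failures, only demographic data are listed |
| SAP 7.7.2 | Medical history is listed for the Safety population, which excludes screen failures |

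An enrolled child's reaction would at least appear in the medical history listing. For a screen failure, the SAP text gives a reaction filed as medical history no stated output.

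**Step 4: serious reactions.** Section 15.2 opens by requiring any serious event to go on both the AE form and the SAE form, without asking whether it was anticipated. It then defines seriousness as a property of an AE or suspected adverse reaction. The text is somewhat ambiguous, but the gap is smaller here than for non-serious events.

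**Step 5: the contraindication.** None of the 8 inclusion or 24 exclusion criteria mentions cosyntropin. Exclusion 16 and Section 6.3 concern the cream and its ingredients. Section 13.5 cites Appendix 4 for how to perform the test and includes no question about a previous reaction. Sections 10.4 and 10.5 schedule the second and later injections without such a question, and Sections 14.2 and 14.4 direct children who withdraw during treatment to the End of Study CST as well.

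**Step 6: scale.** Inputs: about 24 enrolled (Section 14.4) and two scheduled CSTs per treated child.
- Scheduled injections: 24 × 2 = 48
- Before the first dose: 24 / 48 = 50%

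Let S be the number of screen failures who had a CST and F the number of follow-up CSTs in suppressed children; neither is given. The pre-dose share is (24 + S) / (48 + S + F), which is at least 50% whenever S ≥ F.

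**The case against.** The strongest reply is that the plan has more protection than a quick reading suggests. Most of that stands.

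- **A reader might infer that nothing can stop a child who reacted from being injected again.** The documents do not support this. Section 10.2 has the investigator reconfirm eligibility at Baseline, after the Screening CST. Exclusion 10 (any condition making participation unsafe) and inclusion 6 (no clinically relevant abnormality in the medical history, which is where the reaction would be filed) both apply then. Section 14.2 allows withdrawal in the child's best interest, and Section 14.4 rules out a follow-up CST in screen failures on laboratory grounds. What remains is that all these provisions for enrolled children rest on judgement and none names cosyntropin.
- **A reader might infer that the protocol instructs sites to act against the label.** No section directs an injection in a child with a known previous reaction, and the full label is appended. The label also says nothing about how reactions are recorded, so it bears only on the eligibility question.
- **A reader might infer that serious reactions escape SAE reporting.** The opening of Section 15.2 points the other way.
- **A reader might infer that the screen-failure AE summary must be empty.** It need not be: unanticipated procedure-related events are AEs before dosing and could appear there.
- **The data are not wholly lost.** SAP Listing 16.2.6 is not restricted by title to treatment-emergent events, and Protocol Section 18.3.3.5 says all reported AEs are listed. This helps only if the reaction was recorded as an AE in the first place, which is the point in dispute.

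**Conclusion.** The point holds as a conflict within the documents that should be resolved. Read literally, Section 15 sends listed, non-serious reactions to the Screening CST to medical history, while Section 13.5, Section 15's own definition, the Schedule of Events and Section 18.3 treat them as AEs or expect AEs at that stage. The SAP does not carry through the screen-failure AE summary. Separately, the only contraindication in Appendix 4 has no specific counterpart in the eligibility criteria or before any CST; only the investigator-judgement provisions could apply.

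The size is modest: about 24 of 48 scheduled injections, plus those of screen failures, fall before AE collection starts. No event count is claimed, because the documents give no rate and the label describes hypersensitivity as rare. The primary endpoints and the treatment-emergent AE tables do not change.

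The conclusion assumes that being listed in Section 13.5 for the consent/assent form makes a reaction anticipated, and that the interval from consent to first dose is governed by the wash-out and baseline rule. If the second assumption were relaxed, the statement that AE collection starts at first dose would lead to the same place.

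**What to change.** 1. **Protocol Section 15.** Remove the requirement that the event be unanticipated from the recording condition, so that any event after consent that results from a study procedure (CST or venipuncture) is recorded as an AE. Keep reporting to the IRB/IEC as an unanticipated problem for unanticipated events only.
2. **SAP.** Add one listing of pre-treatment AEs that includes screen failures, kept out of the treatment-emergent tables, and bring SAP 7.7.1 into line with Protocol Section 18.3.
3. **Contraindication.** The sponsor should reconcile Sections 5.1.2, 10.4, 10.5 and 13.5 with the contraindication in Appendix 4. How that is done is a clinical decision for the sponsor, and no rule is proposed here.

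The cost is protocol wording, one listing and a few more pre-treatment AE records. Items 1 and 2 need no extra visit or sample.
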